4.2 Inclusion criteria

To be included in the study, patients must meet all of the following criteria:

1. Written informed consent (IC) obtained.
2. Males aged ≥ 18 years.
3. Histologically or cytologically confirmed adenocarcinoma of prostate without neuroendocrine differentiation or small cell features.
4. CRPC defined as 3 rising PSA levels after the nadir taken at least 1 week apart during ADT. If the patient has a history of antiandrogen use, the most recent PSA value must be obtained at least 4 weeks after antiandrogen withdrawal. See Section 0 for further details.
5. Castrate level of serum testosterone (< 1.7 nmol/l [50 ng/dl]) on GnRH agonist or antagonist therapy or after bilateral orchiectomy. Patients who have not undergone bilateral orchiectomy must continue GnRH therapy during the study.
6. PSADT of ≤ 10 months and PSA ≥ 2 ng/ml at screening. See Section 0 for further details.
7. Eastern Cooperative Oncology Group (ECOG) performance status of 0-1.
8. Blood counts at screening: haemoglobin ≥ 9.0 g/dl, absolute neutrophil count $\geq 1500/\mu\text{l}$ ($1.5 \times 10^9/\text{l}$), platelet count $\geq 100,000/\mu\text{l}$ ($100 \times 10^9/\text{l}$) (patient must not have received any growth factor or blood transfusion within 7 days of the haematology laboratory obtained at screening).

9. Screening values of serum alanine aminotransferase (ALT) and aspartate transaminase (AST) ≤ 2.5 x upper limit of normal (ULN), total bilirubin ≤ 1.5 x ULN (except patients with a diagnosis of Gilbert's disease), creatinine ≤ 2.0 x ULN.
10. Sexually active patients, unless surgically sterile, must agree to use condoms as an effective barrier method and refrain from sperm donation during the study treatment and for 3 months after the end of the study treatment.

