4.3 Exclusion criteria

Patients will not be entered into this study if they meet any of the following criteria:

1. History of metastatic disease at any time or presence of detectable metastases by blinded central reading within 42 days prior to start of study treatment. Presence of pelvic lymph nodes < 2 cm in short axis below the aortic bifurcation is allowed. See Section 0 for further details.
2. Symptomatic local-regional disease that requires medical intervention including moderate/severe urinary obstruction or hydronephrosis due to prostate cancer.
3. Acute toxicities of prior treatments and procedures not resolved to grade ≤ 1 or baseline before randomisation.
4. Prior treatment with:
 - second generation AR inhibitors such as enzalutamide, ARN-509, darolutamide, other investigational AR inhibitors,
 - CYP17 enzyme inhibitor such as abiraterone acetate, TAK-700 or
 - oral ketoconazole longer than for 28 days.
5. Use of estrogens or 5- α reductase inhibitors (finasteride, dutasteride) within 28 days before randomisation and AR inhibitors (bicalutamide, flutamide, nilutamide, cyproterone acetate) at least 28 days before screening.
6. Prior chemotherapy or immunotherapy for prostate cancer, except adjuvant/neoadjuvant treatment completed > 2 years before randomisation.
7. Use of systemic corticosteroid with dose greater than the equivalent 10 mg of prednisone/day within 28 days before randomisation.
8. Radiation therapy (external beam radiation therapy [EBRT], brachytherapy, or radiopharmaceuticals) within 12 weeks before randomisation.
9. Severe or uncontrolled concurrent disease, infection or co-morbidity that, in the opinion of the investigator, would make the patient inappropriate for enrolment.
10. Treatment with an osteoclast-targeted therapy (bisphosphonate or denosumab) to prevent skeletal-related events within 12 weeks before randomisation. Patients receiving

osteoclast-targeted therapy to prevent bone loss at a dose and schedule indicated for osteoporosis may continue treatment at the same dose and schedule.

11. Known hypersensitivity to the study treatment or any of its ingredients.
12. Major surgery within 28 days before randomisation.
13. Any of the following within 6 months before randomisation: stroke, myocardial infarction, severe/unstable angina pectoris, coronary/peripheral artery bypass graft; congestive heart failure New York Heart Association (NYHA) Class III or IV.

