6.1.1 Procedures during the screening period (-28 to -1 days)

A prospective study subject will receive both written and verbal information about the study, and will have an opportunity to ask questions and sufficient time to decide whether or not to participate in the study. The original signed and dated IC must be retained in the Investigator's study file and a copy must be provided to the patient.

All patients for whom the IC procedure is completed successfully will be assigned a subject number.

In addition to central laboratory sample collection, a local PSA value should be obtained at screening and used to confirm the patient has CRPC (inclusion criterion 4) and meets inclusion criterion 6.

To define CRPC and fulfil inclusion criterion 4, 3 subsequent PSA values rising after the nadir must be taken when the patient was on androgen deprivation therapy (ADT) that started at least 4 weeks before each PSA sampling, or at least 4 weeks after a bilateral orchiectomy.

PSA values used in calculation of PSADT should preferably have been obtained using the same assay, preferably at the same laboratory. PSADT should not be calculated using PSA values obtained when testosterone is rebounding after ADT (started at least 4 weeks before each PSA sampling, or at least 4 weeks after a bilateral orchiectomy). At least 3 PSA values need to be available and measured over the last 12 months before randomisation, at least 4 weeks apart. Screening PSA from local laboratory must be included in the PSADT calculation. The PSA values used for the calculation must be > 0.2 ng/ml and the screening value ≥ 2 ng/ml. The PSA values used for the calculation of PSADT will be recorded on the CRF.

PSADT will be calculated using a linear regression model of the normal logarithm of PSA and time ([Pound CR et al., 1999](#)). Medical monitor must review the PSA and PSADT values submitted on the eligibility form before randomisation.

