11.2.1.3 Modification 3: Entry criteria updated

Inclusion criterion 4 was modified for clarity. The protocol section providing additional details on the assessment requirements was additionally given for reference.

Inclusion criterion 6 was modified to correct an error with regards to the required PSA value at screening: a value of ≥ 2 ng/ml is required. The protocol section providing additional details on the assessment requirements was additionally given for reference.

Inclusion criterion 9 was modified to correct an error. Both ALT and AST values at screening must be $\leq 2.5 \times$ ULN, not only one of them.

Exclusion criterion 1 was modified for clarification purposes: The time periods for detecting metastases by blinded central reading or a metastatic disease are now specified. The protocol section providing additional details on the assessment requirements was additionally given for reference.

Exclusion criterion 5 was revised to make it consistent with inclusion criterion 4 where a withdrawal period of 4 weeks before screening (instead of before randomisation) is requested.

Exclusion criterion 14 was modified to make it consistent with the rest of the protocol on how to perform the blood pressure measurements.

Exclusion criterion 18 was modified to allow participation of subjects taking part in another interventional clinical trial but who are no longer on study treatment (i.e. subjects in follow-up period). This change is made to clarify that only a wash-out period after any previous investigational treatment is required.

Protocol sections affected: Synopsis, 4.2 Inclusion criteria, 4.3 Exclusion criteria, 5.7.1 Prior and concomitant treatments, 6.1.1 Procedures during the screening period (-28 to -1 days)

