### 6.1.2 Demographic and Baseline Characteristics

Descriptive summaries of demographics and baseline characteristics will be presented by treatment group and overall for the FAS and SAF populations. Comparability of the treatment groups with respect to demographics and baseline characteristics will be assessed using descriptive summaries.

The following demographic data will be summarized:

- Age (years), calculated at the date of randomization using date of birth
- Age (years) (<65, 65 - 74, 75 - 84, ≥85)
- Sex (Male)
- Race (White, Asian, Black or African American, Other)
- Ethnicity (Hispanic or Latino)
- Height (cm)
- Weight (kg)
- Body Mass Index (BMI) (kg/cm^2) (< 20, 20 to < 25, 25 to < 30, ≥ 30)
- Geographical region (North America, Asia Pacific, ROW).

The following baseline characteristics will be summarized:

- PSADT (≤6, >6 months) - IVRS
- PSADT (≤6, >6 months) - CRF
- PSADT (months)
- Osteoclast-Targeted Therapy (yes, no) - IVRS
- Osteoclast-Targeted Therapy (yes, no) - CRF
- ECOG Performance status
- Gleason Score
- Primary tumor classification
- Regional lymph node classification
- Time since start of castration-resistant (months)
- Time since initial diagnosis (capture under clinical staging) (months)

- Time from start of first prior GnRH agonist/antagonist to start of study-drug (months) (for selection, see 9.12)
- Time from prior orchiectomy to start of study-drug (months)
- Time from start of first prior antiandrogen (AR inhibitors) to start of study-drug (months) (for selection, see 9.11)
- Time from the first prior ADT to start of study drug (months) (ADT is defined by GnRH agonist/antagonist, orchiectomy, antiandrogen (AR inhibitors))
- Renal function - eGFR at baseline:
  - Normal:  $eGFR \geq 90$  mL/min
  - Mildly impaired:  $60 \leq eGFR < 90$  mL/min
  - Moderately impaired:  $30 \leq eGFR < 60$  mL/min
  - Severely impaired:  $15 \leq eGFR < 30$  mL/min
  - End stage renal disease:  $eGFR < 15$  mL/min and not on dialysis, or requiring dialysis

eGFR will be calculated according to the Modification of Diet in Renal Disease (MDRD) Formula:

$$eGFR \text{ (mL/min/1.73m}^2\text{)} = 186 \times SCR^{-1.154} \times \text{age}^{-0.203} \times (0.742, \text{ if female}) \times (1.212 \text{ if blacks or African American}) \times (0.881 \text{ if Japanese}) \times (1.227 \text{ for Chinese (mainland China, Taiwan and Hongkong), where SCR= serum creatinine measured in mg/dL}$$

- Hepatic impairment at baseline:

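### Exclusion criterion 5 writes an AR-inhibitor withdrawal requirement as a reason to exclude, so its literal text conflicts with inclusion criterion 4

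*Protocol*

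**What the plan says.** Protocol Section 4.3 opens with "Patients will not be entered into this study if they meet any of the following criteria", so each numbered item is a reason to keep a patient out.

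Criterion 5 has two limbs in one sentence. The first concerns estrogens and 5-alpha reductase inhibitors and ends "finasteride, dutasteride) within 28 days before randomisation". The second, joined by a plain conjunction, concerns "AR inhibitors (bicalutamide, flutamide, nilutamide, cyproterone acetate) at least 28 days before screening". The Synopsis has the same sentence, so neither place corrects the other.

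Inclusion criterion 4 (Section 4.2 and Synopsis) deals with the same patients from the other side. For a man with a history of antiandrogen use, it requires that "the most recent PSA value must be obtained at least 4 weeks after antiandrogen withdrawal". Section 6.1.1 ties this to the screening sample: "a local PSA value should be obtained at screening and used to confirm the patient has CRPC (inclusion criterion 4").

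SAP v4.2 expects such patients in the trial. Section 6.1.2 plans to summarise "Time from start of first prior antiandrogen (AR inhibitors) to start of study-drug (months"), and Section 9.11 defines antiandrogens by codes that include the four drugs named in criterion 5.

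**The concern.** An exclusion with a time window normally names recent exposure. The AR-inhibitor limb instead names exposure that lies at least a minimum time in the past. That wording would suit an inclusion list, where it would state a condition to be satisfied. In an exclusion list it turns the condition round, so satisfying it bars the patient.

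The text is operative. Section 5.4.2 makes randomisation depend on meeting every inclusion criterion and no exclusion criterion, and Section 4.6 requires the criterion causing exclusion to be recorded for screening failures. Anyone who follows criterion 5 as written gets an answer that inclusion criterion 4 contradicts, and a description of eligibility copied from Section 4.3 would misstate the intended population.

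**Working it through.** No sample size, event count or significance level is involved, so the check is a logical comparison of the two criteria. The time units agree: 4 weeks × 7 days = 28 days.

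**Step 1: patient by patient.** I take the first limb (estrogens, 5-alpha reductase inhibitors) as not met, read the second limb as a separate reason to exclude, and treat the date of the screening PSA as the date of screening.

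| AR-inhibitor history | Exclusion 5, second limb, literal | Inclusion 4, antiandrogen clause |
|---|---|---|
| (a) Use ended 28 or more days before screening | Met: barred | Satisfied |
| (b) Only use began within the 28 days before screening | Not met: not barred | Not satisfied: the screening PSA falls less than 4 weeks after withdrawal |
| (c) Use began 28 or more days before screening and continued into the last 28 days | Met through the earlier use: barred | Not satisfied, for the same reason as (b) |
| (d) Never used | Not met | Clause does not apply |

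In (a) and (b) the two criteria give opposite answers. In (c) they agree, though criterion 5 reaches the result only through the earlier exposure. Applied together literally, they leave essentially no prior AR-inhibitor user eligible: (a) falls to exclusion 5, (b) to inclusion 4, and (c) to both. The practical weight lies in (a), because inclusion 4 already stops (b).

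**Step 2: the other way to parse the sentence.** If the conjunction requires both kinds of use, a patient in row (a) is barred only if he also took an estrogen or a 5-alpha reductase inhibitor in the 28 days before randomisation. That removes the conflict for most of row (a), but it breaks the first limb: a recent estrogen user with no AR-inhibitor history would no longer be barred. Neither parse gives a coherent criterion.

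**Step 3: comparison within Section 4.3.** The first limb of criterion 5 and criteria 7, 8, 10, 12, 13 and 18 all exclude exposure or events within a stated period before randomisation. Where a minimum elapsed time appears elsewhere (criteria 6 and 15), it describes patients excepted from the exclusion. The AR-inhibitor limb is the only place where a minimum elapsed time is itself the ground for exclusion.

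**Step 4: evidence of purpose.** The amendment history (Section 11.2.1.3) says criterion 5 was revised for consistency with inclusion criterion 4, "where a withdrawal period of 4 weeks before screening (instead of before randomisation) is requested". That log is corroboration only. Inclusion criterion 4, which is current text, points the same way.

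**The case against.** The strongest reply is that no competent reader would be misled. Inclusion criterion 4 shows the intent, the amendment history confirms it, and under Section 5.4.2 the medical monitor reviews and approves each eligibility form before randomisation. Nothing in the documents suggests that the literal reading was applied. This stands, and it limits the consequence. It does not make the sentence correct: a rule that has to be read against its own wording should be reworded.

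Four stronger readings are tempting, and the documents do not support them.

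- **That criterion 5 lets recent users in.** A long-term user who stopped shortly before screening did use the drug 28 or more days before screening, so the literal text bars him (row c). Only row (b) escapes criterion 5, and inclusion criterion 4 with the screening PSA stops that group.
- **That eligibility deviations would be coded differently from site to site.** Approval before randomisation is central. SAP Sections 4.6.1 to 4.6.3 place major deviations under sponsor criteria, a separate deviations document and blinded review.
- **That the subgroup with two or more prior hormonal therapies (SAP Section 6.2.4) would be nearly emptied.** SAP Section 9.13 also counts GnRH agents as hormonal therapy and does not say whether therapies are counted by agent or by class. Patients might therefore reach two without an AR inhibitor.
- **That the efficacy analysis is affected.** SAP Section 5 defines the full analysis set as all randomised patients and drops the per-protocol set. Eligibility coding cannot move anyone into or out of the MFS or OS analysis.

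**Conclusion.** This is an internal inconsistency in a current eligibility criterion, and it is wrong as written. The AR-inhibitor limb of exclusion criterion 5 bars patients for whom inclusion criterion 4 provides and whom the SAP plans to describe. It also leaves the narrow group in row (b) to be caught by inclusion criterion 4 alone.

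The size cannot be computed, because the documents do not give the proportion of patients with prior AR-inhibitor use. The consequence runs from none, if everyone followed the evident intent, to wrongful exclusion of every patient whose use ended 28 or more days before screening, if the sentence were applied literally. The documents give more reason to expect the former. Power, alpha and the full analysis set are untouched.

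The conclusion rests on two assumptions: that the second limb is a separate ground for exclusion, and that the screening PSA is dated at screening. The first matters little, since the alternative parse fails in another way. The second affects only how completely inclusion criterion 4 stops rows (b) and (c). It does not affect row (a).

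**What to change.** The sponsor should reconcile exclusion criterion 5 with inclusion criterion 4 in both the Synopsis and Section 4.3. Split criterion 5 into two separately stated clauses, so that the conjunction no longer carries meaning, and word the AR-inhibitor clause so that its direction agrees with inclusion criterion 4. Which interval and reference date apply is for the sponsor to confirm; no new withdrawal rule is proposed here.

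Eligibility deviations should be assessed against the reconciled text, and the deviations document checked for the same inverted wording. The SAP supplement covers a report addendum written after all patients have discontinued, so by then the remaining benefit lies mainly in deviation assessment and in describing the enrolled population accurately.

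The cost is one sentence in two places. No analysis, dataset or sample size changes.

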4.4 Screening log and subject identification list

The investigator will keep appropriate source records to detail patients.

Patient's full identity including name and address is captured in a log named e.g. subject identification list, which is filed in an Investigator's study file and never shared outside. The screening log captures patient's subject number, year of birth, screening date, randomisation date and reason for screen failure where applicable. Patient's initials and full date of birth will not be captured on the screening log.

No identifying information will be collected on the pre-screening log on patients who were considered for the study but did not consent.

4.5 Recruitment procedures

Detailed recruitment procedures will be presented in a separate document.

From the local study centre's patient population, the investigator will identify and approach

potential candidates for screening and possible enrolment. In addition to this, patients will be invited to participate in the study during routine follow-up visits or telephone contacts by physicians. In countries where advertisements are permitted, patients will be invited via such advertisements in local newspapers, patient newsletters (or related publications) or appropriate websites. Only text as accepted by independent ethics committees (IECs) or independent review boards (IRBs) will be used in any advertisement media.

Patients who are not eligible for the study will be informed and the reason for their exclusion will be explained, including information on which eligibility criterion led to their exclusion from the study.

If patients discontinue their participation in the study, they are not allowed to re-enter the study.

4.6 Information to be collected on screening failures

The minimum information to be collected on patients who have been screened but not randomised will include completion of the following case report form (CRF) fields: IC, demography (date of birth and sex), the inclusion/exclusion criteria causing the exclusion, decision of entry, AEs related to study procedures and all SAEs (including all information related to these events, such as concomitant treatments, medical history and other relevant information).

4.7 Discontinuation of study and withdrawal from study treatment

4.7.1 Reasons for discontinuation of study

Patients are free to discontinue the study at any time for any reason. Investigators should try to find out the reason and document it on the corresponding CRF (study completion/discontinuation). Additionally, the investigator may withdraw a patient at any time if he/she considers this to be medically necessary and in the patient's best interest.

In case the patient will initiate any prohibited treatment (see Section 5.7.2) before confirmed metastasis during the double-blind treatment, the patient must discontinue the study treatment and they will be followed for survival until the end of the study.

In case the patient will initiate any prohibited treatment (see Section 5.7.2) during the open-label treatment phase before metastasis confirmed by local reading, the patient must discontinue the study treatment and they will be followed for survival until the end of the study.

Patients will be invited to the end-of-study treatment visit 28 days after the last dose of study treatment. Another systemic antineoplastic therapy may be initiated no sooner than 7 days after the last dose of study treatment.

4.7.2 Reasons for withdrawal from study treatment

Patients must be withdrawn from study treatment for the following reasons:

- Confirmed metastasis (in the double-blind treatment phase) (see Section 4.7.2.1)
- Metastasis identified by local reading (in the open-label treatment phase) (see Section 4.7.2.1)
- Intolerable AE (see Section 4.7.2.2)

The study monitor and medical monitor should be notified about study treatment withdrawals by email/phone/fax within 24 hours in the event of discontinuation due to an SAE or within 7 days in the event of discontinuation due to another reason.

Patients will be invited to the end-of-study treatment visit 28 days after the last dose of study treatment.

Patients withdrawing from study treatment before metastasis during the double-blind or open-label darolutamide treatment phase (e.g., toxicity, clinical progression, judgment of the investigator) with or without receiving subsequent prohibited antineoplastic therapy will be followed as outlined in Table 4 until the end of the study.

Patients who discontinue darolutamide during the open-label darolutamide treatment phase without metastases and who withdraw consent to study procedures but agree to follow-up for survival will be followed via phone for survival status until the end of the study.

Patients, after confirmed metastasis or receiving subsequent treatment after unblinding, will be followed as outlined in Table 4 until the end of the study.

After the end-of-study treatment visit, the patients will be followed every 16 weeks by visit or telephone contact until the end of study as outlined in Table 4 and Sections 6.1.2.6 and 6.1.3.

